#### **Materials and Methods**

#### Patients and study design

This was a randomized controlled trial. The sample size was determined using two samples t-test power calculation. The 1 log increase of serum HBV DNA level was defined as a significant difference between two samples. Effect size (Cohen'd=0.39) was obtained using two parameters including difference and standard deviation. The power and a significant level were set as 0.8 and 0.05, respectively. The sample size was calculated out as 82 in each group. The ratio of exclusion was estimated as 20 %. Therefore, the sample size was set as 196 in this clinical trial. In our clinical experience, the majority of vitamin D deficiency patients can achieve adequate serum vitamin D levels after two months vitamin D supplement. Furthermore, the liver dysfunction due to hepatitis flare or cirrhosis could be a confounding factor for the low serum vitamin D levels in HBV-infected patients. According to the above consideration, our study was designed to enroll 196 non-cirrhotic, HBV-infected patients with normal or minimally elevated serum ALT levels. Thus, chronic HBV patients receiving regular 6-month surveillance and without current antiviral treatment in the outpatient clinic of Taipei Tzu Chi Hospital were invited to join the study from

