August 2017 to September 2018. All had positive hepatitis B surface antigen (HBsAg) for more than 6 months. Those with positive anti-hepatitis C virus (HCV) antibody, alcoholic liver disease, other known causes of chronic hepatitis or hepatocellular carcinoma were excluded. Cirrhosis was diagnosed based on histological findings or ultrasonographic evidence of nodular liver surface with coarse echotexture and splenomegaly. After obtaining written informed consent, levels of serum vitamin D, HBV DNA and quantitative HBsAg (qHBsAg) levels were measured. Those who had HBsAg loss, undetectable HBV DNA and adequate vitamin D level (≥30 ng/mL) were excluded. The eligible subjects were randomized into two groups by using the computer random distribution. Patients in the vitamin D group received vitamin D supplement (D3, 2000 IU/day; Metagenics, Aliso Viejo, CA 92656) for 2 months and untreated patients were used as the control group. Levels of vitamin D, HBV DNA and qHBsAg before and after 2 months of treatment or follow-up were compared between these two groups. The primary endpoint was to identify any difference between two groups. Patients lost to follow-up or poor drug compliance (vitamin D intake amount < 80%) were excluded for per-protocol analysis. Both intention-to-treat and per-protocol analyses were conducted.

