# Laboratory testing

Serum aspartate aminotransferase (AST) and alanine aminotransferase (ALT) were measured using routine automated methods (Dimension Flex®reagent cartridge, USA; SIEMENS, Dimension, NY, USA). The upper limit of normal of ALT was 63 U/L in men and 59 U/L in women. The HBeAg and Anti-HCV were assayed using Abbott ARCHITECT, Wiesbaden, Germany. The Fibrosis 4 index (FIB-4) was calculated base on the formula: FIB-4=Age (years)×AST (U/L)/[PLT(109/L)×ALT1/2(U/L)]. Based on our previous study, FIB-4 >= 0.87 was defined as the presence of significant fibrosis (>=F2).

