Title: The causal relationship between serum vitamin D level

and hepatitis B virus replication in patients with chronic

hepatitis B virus infection

NCT 03068767

Date of document: 1, June 2017

IRB approval letter (as attached)

Statistical Analyses Plan

Statistical analysis was performed using SPSS version 16.0 (SPSS Inc. Chicago, IL).

Data were analyzed by chi-square test and student's t test. The correlation among

serum vitamin D and FIB-4 was analyzed using Pearson's correlation analysis. The

significance in all of the tests was two-tailed and a p value of less than 0.05 was

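### HBV DNA is known before allocation, but no stratification is described and the visible SAP names no baseline adjustment, at a cost in precision and readability

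*Protocol*

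**What the plan says.** All of the protocol's design text on this point is under Patients and study design. The order of events is consent, then testing ("After obtaining written informed consent, levels of serum vitamin D, HBV DNA and quantitative HBsAg (qHBsAg) levels were measured"), then exclusion on those results ("Those who had HBsAg loss, undetectable HBV DNA and adequate vitamin D level (≥30 ng/mL) were excluded"), then allocation: "The eligible subjects were randomized into two groups by using the computer random distribution". Strata, blocks, minimisation and an allocation ratio are not mentioned there or in the SAP.

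HBeAg appears once, under Laboratory testing: "The HBeAg and Anti-HCV were assayed using Abbott ARCHITECT, Wiesbaden, Germany". No timing is given, and HBeAg is not among the markers listed as measured after consent.

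The sample-size paragraph takes 1 log of HBV DNA as the difference of interest and adds that "Effect size (Cohen'd=0.39) was obtained using two parameters including difference and standard deviation". It does not say whether the SD is that of level or of change. It gives 82 per group, a 20% allowance and a total of 196.

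The between-group comparison covers levels before and after 2 months. Whether the test is of follow-up level or of change is not stated. The visible SAP text lists chi-square, Student's t and Pearson correlation, and no model with a baseline covariate.

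**The concern.** Baseline HBV DNA is likely to be among the strongest predictors of HBV DNA two months later in untreated carriers. Eligibility sets a floor (HBV DNA must be detectable) but no ceiling, so starting values may spread widely. The value is in hand for every patient at allocation, yet neither the described allocation nor the visible analysis uses it.

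Two things are at stake. The first is precision: an unadjusted t test on follow-up level leaves all the between-patient spread in the error term. The second is how one realised trial can be read. If the arms happen to start half a log apart and only follow-up level is compared, much of that gap reappears at 2 months against a target of 1 log, and the reader cannot easily separate it from an effect of supplementation.

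**Working it through.** **Inputs.** From the protocol's sample-size paragraph: difference 1 log, d = 0.39, power 0.80, significance level 0.05, 82 per group, 20% allowance, total 196. Equal allocation (98 per arm) is assumed from the equal group sizes.

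**The plan's own figure.** Per group, n = 2(z_α + z_β)²/d².
- One-sided 5%: 2 × (1.645 + 0.842)²/0.39² = 81.3, so 82. This reproduces the stated figure (exact t solution 81.98).
- Two-sided 5%: 2 × (1.960 + 0.842)²/0.39² = 103.2, so 104. The SAP's tests are two-tailed; that mismatch is a separate matter and is not used below.
- Total: 82 × 1.2 = 98.4, taken as 98 per arm, gives 196.

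**Implied SD.** 1/0.39 = 2.56 log10. The next steps assume that this is the between-patient SD of baseline level.

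**Chance of a starting gap above 0.5 log, either direction.** SE = SD × √(2/n) and P = 2 × P(Z > 0.5/SE).
- 98 per arm: SE = 2.564 × √(2/98) = 0.366; 0.5/0.366 = 1.365; P = 17.2%.
- 82 per arm: SE = 2.564 × √(2/82) = 0.400; 0.5/0.400 = 1.25; P = 21.2%.
- A gap above 1 log has probability 0.6% (98 per arm) or 1.3% (82 per arm).

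**Sensitivity to the SD.**

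| Baseline SD (log10) | 98 per arm | 82 per arm |
|---|---|---|
| 1.5 | 2.0% | 3.3% |
| 2.0 | 8.0% | 10.9% |
| 2.56 | 17.2% | 21.2% |
| 3.0 | 24.3% | 28.6% |

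**What a gap does to the comparison.** The documents give no correlation ρ between baseline and 2-month log10 HBV DNA. Assume ρ = 0.9, range 0.7 to 0.95, with equal SDs at both times. With no treatment effect, a 0.5-log gap carries 0.5ρ into follow-up level: 0.45 log (0.35 to 0.475). A test of change leaves 0.5(1 − ρ), in the opposite direction: 0.05 log (0.15 to 0.025).

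**Precision at 98 per arm, SD 2.56.** Relative to follow-up level, the SE is multiplied by √(2(1 − ρ)) for change and by √(1 − ρ²) for ANCOVA.

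| ρ | Follow-up level | Change | ANCOVA |
|---|---|---|---|
| 0.7 | 0.366 | 0.284 | 0.262 |
| 0.9 | 0.366 | 0.164 | 0.160 |
| 0.95 | 0.366 | 0.116 | 0.114 |

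**Effect of stratifying.** With a median split of a normal baseline, the within-stratum SD is √(1 − 2/π) = 0.603 of the total. At 98 per arm the SE becomes 0.603 × 0.366 = 0.221, and 0.5/0.221 = 2.26 gives 2.4%. At 82 per arm it becomes 0.603 × 0.400 = 0.241, giving 3.8%. A simulation of 20,000 trials with balanced allocation within strata gave the same 2.4% and 3.8%.

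**The case against.** The strongest reply is that randomisation already deals with this. Chance imbalance does not bias the comparison, and if 2.56 is the SD of level, that spread is already in the t test's standard error and in the sample size. This stands: the loss is of precision and credibility, not validity.

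Second, the 17% rests on reading 2.56 as the SD of baseline level. The protocol's wording, "The 1 log increase of serum HBV DNA level was defined as a significant difference between two samples", can be read as change. If it is the SD of change, the documents give no baseline SD, and only the sensitivity range remains. This also stands.

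Third, the comparison may be of change, in which case most of the level gap cancels. That is true, but the documents do not settle it.

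Fourth, baseline adjustment alone would do most of the work. This is largely right. At 98 per arm, a 0.5-log gap raises the variance of an ANCOVA estimate by a factor of only about 1 + 1.365²/194 = 1.01. But no such adjustment is named, and stratifying on a value already available adds protection at little cost.

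A reader might also infer several stronger points that the documents do not support:
- **That no strata or blocks were used.** The text is silent; the phrase about computer randomisation excludes neither.
- **That HBeAg was known before allocation.** Its timing is not stated.
- **That imbalance is a 1-in-5 risk.** That figure belongs to the 82 evaluable; imbalance at randomisation is governed by the 98 allocated, nearer 1 in 6, and both depend on the SD assumption.
- **That the arm ratio drifts across seasons.** This presumes no blocking, and random drift would not be systematic bias.

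**Conclusion.** The point holds as a modest improvement to the design and analysis. A baseline value of the outcome is available before allocation, and neither the described randomisation nor the visible analysis uses it. If the implied 2.56 log10 is the SD of baseline level and allocation is equal, the chance of a starting gap above 0.5 log is about 17% as randomised and 21% among the planned evaluable patients. Across SDs of 1.5 to 3.0 it runs from about 2% to 24% at 98 per arm.

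The consequence is lost precision and, if follow-up level is tested, a result that is hard to interpret when a gap occurs. One might be tempted to conclude that the trial is biased or its false-positive rate raised. The documents do not support that: under valid randomisation the overall type I error is unaffected.

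**What to change.** 1. State the allocation method. Use computer-generated permuted blocks of varying size, stratified by baseline HBV DNA in two bands, with a cut-point fixed in advance near the expected median. The fall to about 2% to 4% assumes a median split and SD 2.56; a cut-point far from the median would gain less.
2. Make the primary comparison an ANCOVA of 2-month log10 HBV DNA between arms, with continuous baseline log10 HBV DNA and the stratum as covariates. This also settles whether level or change is tested.
3. Add HBeAg as a stratum only if its result is available before allocation; otherwise enter baseline HBeAg as a covariate.

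The cost is a slightly more complex allocation list at one centre and a slightly more complex analysis. Stratifying by HBV DNA needs no extra test. If allocation has already been made, report how it was done and adopt the ANCOVA before outcomes are compared by arm; that secures most of the gain.

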# **Abstract**

**Background and Aims:** Vitamin D deficiency is common in patients with chronic hepatitis B virus (HBV) infection. Previous study showed an inverse association between vitamin D and HBV DNA levels. However, the causal relationship between vitamin D and HBV replication remains inconclusive.

Methods: HBV carriers receiving regular 6-month surveillance without current antiviral treatment or cirrhosis were invited to participate into this trial. The markers of HBV replication included serum HBV DNA and quantitative HBsAg (qHBsAg) levels. Those with undetectable HBV DNA or sufficient vitamin D levels, cancer or electrolyte imbalance were excluded. The eligible subjects were randomized to receive either vitamin D supplement 2000 IU per day for 2 months (vitamin D group) or none (control group). Levels of vitamin D, HBV DNA and qHBsAg before and after 2 months of treatment or follow-up were compared between these two groups. The primary endpoint was to identify any difference between two groups.

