# Introduction

Hepatitis B virus (HBV) infection is a global health problem, especially in Taiwan. The clinical manifestations of HBV infection include acute/fulminant hepatitis or various forms of chronic infection. Chronic HBV infection may lead to inactive carrier, chronic hepatitis, liver cirrhosis, or hepatocellular carcinoma (HCC). Low vitamin D is frequently found in patients with chronic hepatitis B (CHB) than healthy controls. Furthermore, several cross-sectional studies showed an inverse association between serum vitamin D level and HBV DNA level. However, the causal relationship cannot be confirmed from these studies.

Cholecalciferol is the precursor of the bioactive vitamin D. It is rare in natural foods and the major source is synthesized in the skin during exposure to sunlight. It is hydroxylated in liver to calcidiol, which is released into the plasma and exerts its biological functions by signaling through a nuclear vitamin D receptor. Therefore, liver has a close relationship with the synthesis of vitamin D. Vitamin D plays a crucial role in the bone metabolism and affect immune function not only in innate but also in adaptive immunity. In clinical practice, low vitamin D is associated with autoimmune, infective disease, and the development of malignancy.

Vitamin D has been reported to be an important immune modulator of hepatitis C virus (HCV) infection and metabolic liver disease. 15-20 Regarding HBV-infected patients, the relationship among vitamin D level, HBV viral load and liver dysfunction remains largely unclear. To clarify the causal relationship, we conducted a randomized controlled trial of providing vitamin D supplement to HBV patients with insufficient vitamin D (<30 ng/mL) level to investigate the effect of vitamin D level on HBV replication in terms of HBV DNA and qHBsAg levels.

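### The primary endpoint is any between-group difference: no variable, contrast or analysis set is designated primary, and the visible SAP text gives no testing order

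*Protocol*

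**What the plan says.** The endpoint sentence appears in the Abstract and again under Patients and study design: "The primary endpoint was to identify any difference between two groups". In the latter section the sentence just before it is "Levels of vitamin D, HBV DNA and qHBsAg before and after 2 months of treatment or follow-up were compared between these two groups". That gives three variables and a time point. It does not say whether the arms are compared on the 2-month value or on the change from baseline.

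The two viral markers are presented as equals. The Abstract has "The markers of HBV replication included serum HBV DNA and quantitative HBsAg (qHBsAg) levels", and the Introduction gives the aim as "to investigate the effect of vitamin D level on HBV replication in terms of HBV DNA and qHBsAg levels".

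There are two analysis sets. The PP set is defined by "Patients lost to follow-up or poor drug compliance (vitamin D intake amount < 80%) were excluded for per-protocol analysis", followed by "Both intention-to-treat and per-protocol analyses were conducted". Neither set is ranked above the other.

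The one sign of priority is in the sample-size text: "The 1 log increase of serum HBV DNA level was defined as a significant difference between two samples".

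The SAP says "Data were analyzed by chi-square test and student's t test", adds a Pearson correlation of vitamin D with FIB-4, and sets two-tailed 0.05 for all tests. Its visible text ties no test to an endpoint and gives no order or division of alpha. That text breaks off mid-sentence, so the point rests on the protocol's endpoint sentence, which is complete.

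**The concern.** A primary endpoint should identify the one result that decides the trial. This one can be met in several ways, and nothing written in advance says which counts. Two consequences follow.

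- **Error rate.** If either viral marker, either set or either contrast may carry the claim, the chance of a false-positive primary result is above 0.05.
- **Choice after the fact.** The deciding variable, contrast and set can be picked once the results are known, and a reader could not tell.

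The wording also admits a result that does not address the question. Serum vitamin D is one of the listed variables, and the protocol expects most deficient patients to reach adequate levels on the supplement. A between-group difference in vitamin D is therefore expected, and read literally it would meet the endpoint with no effect on HBV replication.

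**Working it through.** **The plan's own figure.** Inputs from the sample-size text: d = 0.39, power 0.80, significance level 0.05, two-sample t test.

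- One-sided: n = 2(1.645 + 0.842)²/0.39² = 81.3, so 82 per group. This matches the plan.
- Two-sided: n = 2(1.960 + 0.842)²/0.39² = 103.2, so 104 per group (105 by the exact t calculation). This does not match.
- Total: 82 × 1.2 = 98.4, taken as 98 per group, gives 196.

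The mismatch with the SAP's two-tailed rule is a separate matter. What counts here is that the calculation allows for one test on one variable, with the full 0.05 spent on it.

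**Error rates if either result counts.** All figures assume no true effect on the viral markers and two-sided 0.05 per test. The documents give no correlations and no exclusion rates by arm, so those are assumed and shown as ranges. Vitamin D is left out because it is expected to differ.

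For two test statistics with correlation r, the error rate is 1 − P(|Z1| < 1.96 and |Z2| < 1.96), bivariate normal.

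*(1) Either viral marker, one set*

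| Marker correlation r | 0 | 0.5 | 0.7 | 0.9 |
|---|---|---|---|---|
| Error rate | 9.75% | 9.07% | 8.35% | 7.04% |

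*(2) One marker, ITT or PP.* Suppose PP keeps a random fraction f of the vitamin D arm and all controls. Then corr(ITT, PP) = √(2/(1/f + 1)).

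- f = 0.8: √(2/2.25) = 0.943, error rate 6.56%.
- f = 0.9: √(2/2.111) = 0.973, error rate 6.07%.

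*(3) Either marker in either set.* Four statistics, with correlation matrix equal to the Kronecker product of the marker and set matrices.

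| Marker correlation r | 0 | 0.5 | 0.7 | 0.9 |
|---|---|---|---|---|
| 20% of vitamin D arm dropped | 12.7% | 11.8% | 10.8% | 9.1% |
| 10% of vitamin D arm dropped | 11.8% | 10.9% | 10.0% | 8.5% |

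Patient-level simulation with t tests, 98 per arm and 200,000 trials, at r = 0, 0.5 and 0.9 gives 12.6%, 11.8%, 9.1% (20% dropped) and 11.8%, 10.8%, 8.5% (10% dropped).

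*(4) HBV DNA alone, one set, 2-month level or change.* With equal SDs at both times and baseline to 2-month correlation b, corr(level, change) = √((1 − b)/2).

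| b | 0.5 | 0.8 | 0.9 |
|---|---|---|---|
| corr(level, change) | 0.500 | 0.316 | 0.224 |
| Error rate | 9.07% | 9.49% | 9.62% |

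**The case against.** The strongest reply is that HBV DNA is plainly the intended primary. It is the only variable given a relevant difference, and the effect size and power target come from the same calculation. If so, the inflation from two markers disappears. The word for an increase in that sentence might also point to change from baseline, which would settle the contrast.

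This is a fair inference but not a designation. The Abstract and Introduction put qHBsAg on the same footing as HBV DNA. The sizing sentence also speaks of a difference between two samples, which fits a comparison of levels as well as of changes. Granting HBV DNA still leaves the contrast and the analysis set open, and item (4) shows that the contrast alone takes the rate above 9%.

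Three narrower objections stand in part.

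- **The percentages rest on assumptions.** This is so for all of them. The set-choice figures are the weakest. Non-compliers are unlikely to be a random subset. Patients lost to follow-up can come from either arm, and they separate ITT from PP only if ITT imputes their values. Random loss from both arms gives corr(ITT, PP) = √f, hence 6.5% (10% lost) or 7.1% (20% lost) for one marker. Set choice alone therefore adds only about 1 to 2 percentage points.
- **The SAP text is cut off.** A testing order cannot be ruled out from it, so its silence carries little weight.
- **Other rules would also work.** Requiring both markers to succeed in one set, with one contrast, causes no inflation. Nor does a split of alpha across the two markers. The defect is that no rule is stated.

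**Conclusion.** The concern holds. The endpoint sentence, followed literally, lets either viral marker in either set, or the expected rise in vitamin D, count as primary success, and the documents state no rule that would prevent this. The marker choice and the level-or-change choice matter most, each taking a nominal 5% to roughly 7% to 10%. The two markers and two sets together give 8.5% to 12.7%. These figures hold only if either result may count, and they depend on the assumed correlations and exclusion rates. There would be no inflation if one variable, contrast and set had always been the sole primary, or if both markers had to succeed in one set on one contrast. A reader cannot tell which case applies. Because the gap is in the primary endpoint itself, it must be fixed.

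**What to change.** Replace the endpoint sentence in both places in the protocol, and add to the SAP, wording such as: *The primary endpoint is the between-group difference in change from baseline in log10 HBV DNA at 2 months in the ITT set, two-sided alpha 0.05.* Then:

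- preferably adjust for baseline HBV DNA, which is already collected; an unadjusted t test of the change also cures the defect;
- test qHBsAg as a secondary endpoint, only if the primary is significant;
- label PP as supportive;
- report serum vitamin D as a check on the intervention, not as an efficacy endpoint.

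The cost is wording, with no new data and no extra patients on this account. The SAP's t test serves the unadjusted version; adjustment adds one model. The downside is that an effect on qHBsAg alone could not be claimed as primary.

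If the sponsor wants both markers as primary, it should state whether both must succeed or how alpha is split. At two-sided 0.025 each and d = 0.39, n = 2(2.241 + 0.842)²/0.39² = 125 per group (127 by exact t), before any allowance for exclusions.

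Whichever rule is chosen must be fixed before outcomes are compared between arms. The protocol describes recruitment to September 2018 in the past tense. If results have already been seen, the choice should be reported as made afterwards, since naming a primary then does not restore error control.

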# Laboratory testing

Serum aspartate aminotransferase (AST) and alanine aminotransferase (ALT) were measured using routine automated methods (Dimension Flex®reagent cartridge, USA; SIEMENS, Dimension, NY, USA). The upper limit of normal of ALT was 63 U/L in men and 59 U/L in women. The HBeAg and Anti-HCV were assayed using Abbott ARCHITECT, Wiesbaden, Germany. The Fibrosis 4 index (FIB-4) was calculated base on the formula: FIB-4=Age (years)×AST (U/L)/[PLT(109/L)×ALT1/2(U/L)]. Based on our previous study, FIB-4 >= 0.87 was defined as the presence of significant fibrosis (>=F2).

